4.10.5 Trial requirement for HDM from NHS Human Milk Banks

There are 17 human milk banks in the UK. A recent survey of human milk bank service provision in the UK (61) showed that the annual median number of donor mothers to the milk bank was 48, and the annual median number of litres of donor milk pasteurised by each milk bank was 206. It is anticipated that the provision of HDM from the Countess of Chester Human milk bank will match the demand for the purposes of this pilot trial. This Human milk bank currently provides all HDM for Chelsea and Westminster Hospital Neonatal Unit. This study will provide an estimate of trial annual requirement of HDM from NHS human milk banks from data collected on HDM volume requirements of each infant in the HDM feeding arm. This estimate could then be compared to the current service provision of UK human milk banks.

4.10.6 Electronic outcome data capture

Test that outcome data can be retrieved from operational NHS electronic records, thus minimising the burden of data capture and facilitating the use of linked NHS records to achieve long-term follow-up at low cost; data will be captured as detailed above in all randomised babies to discharge. The National Neonatal Research Database is created at the Neonatal Data Analysis Unit from electronic records captured at the point of care on all admissions to neonatal units nationally; the Neonatal Data Analysis Unit is based at Chelsea & Westminster Hospital and led by [name].

4.11 Statistical considerations

4.11.1 Sample size

Statistical considerations have been overseen by the Neonatal Data Analysis Unit Statistician [name]. This study is primarily a feasibility pilot trial and has been designed as such. It is unknown what constitutes a clinically relevant difference in the primary outcome total body adiposity, as measured by whole body MRI, following HDM and PTF supplemented MOM in preterm infants from birth to discharge. Indeed, one of the aims of the study is to obtain data on the magnitude of effect on total body adiposity. However, an estimate of a clinically relevant difference has been made from one previous study using a different method of body composition measurement. In

an observational study, Pielat et al (22) investigated change in body composition, measured using dual energy x-ray absorptiometry at birth and again at discharge, in preterm infants fed with fortified HDM or PTF to supplement MOM. Whole body composition was similar in the two groups at the initial measurement, but differed significantly at the time of the second measurement. They calculated that at the 5% significance level and 80% power, the minimal detectable difference in fat mass would be 86g or 96cc between groups for a total sample size of 40 (20 in each group).

Using our group's database of preterm infants at term age equivalent (July 2012), the mean (standard deviation) of directly measured total body adiposity, using whole body MRI is 0.677(0.243)l. Although the clinically relevant difference may be less than this, we have based our sample size on detecting a one standard deviation difference. A sample size of 22 infants in each group would enable us to detect a 0.243l difference in adiposity between groups with just over 80% power and at 5% significance level. Assuming 10% mortality prior to term and 10% drop out rate, 28 infants will be recruited in to each of the three groups or until 22 infants in each group has had their MRI and MRS at term age equivalent, a total of 66 scans. Thus, over a recruitment period of 18 months, with an estimated recruitment rate of 2-4 infants per month it is realised that the study will likely be underpowered for the outcome of total body adiposity. This sample size is based on single centre recruitment. In the eventuality of one or more centres being involved in the study, the following table has been constructed to demonstrate sample sizes and powers required for detecting a range of possible clinically significant differences in total body adiposity, for which the Bonferroni correction has been used for multiple testing.

Table 3. Power to detect possible clinically relevant differences in adiposity for different sample sizes; AT=adipose tissue; l=litre

| Total n | Power (%) to detect 0.096(l) diff in AT | Power (%) to detect 0.243(l) (1 sd) diff in AT | Difference (l) in AT at 80% power |
|---------|---|--|-----------------------------------|
| 60 | 12.8 | 78.1 | 0.249 |
| 66 | 14.1 | 82.4 | 0.237 |
| 75 | 16.1 | 87.5 | 0.222 |
| 90 | 19.6 | 93.1 | 0.203 |
| 96 | 21 | 94.7 | 0.197 |
| 105 | 23.1 | 96.4 | 0.188 |
| 120 | 26.8 | 98.1 | 0.176 |
| 135 | 30.4 | 99.1 | 0.166 |
| 150 | 34 | 99.6 | 0.157 |
| 165 | 37.6 | 99.8 | 0.15 |
| 180 | 41.2 | 99.9 | 0.144 |
| 210 | 48 | 100 | 0.133 |
| 225 | 51.3 | | 0.129 |
| 240 | 54.5 | | 0.125 |

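### Table 3 rests on a normal approximation; for the Bonferroni-corrected pairwise comparisons it describes, power at the chosen 66 scans is about 80% rather than 82.4%, leaving essentially no margin

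*Combined protocol and SAP*

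**What the plan says.** Section 4.11.1 takes the mean and SD of total body adiposity at term equivalent age from the group's own database: "using whole body MRI is 0.677(0.243)l". On the effect size it says "we have based our sample size on detecting a one standard deviation difference". It then claims that 22 infants per group "would enable us to detect a 0.243l difference in adiposity between groups with just over 80% power and at 5% significance level". Recruitment is to run to 28 per group, or "until 22 infants in each group has had their MRI and MRS at term age equivalent, a total of 66 scans".

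Table 3 follows, for use if further centres join, and is described as a table "for which the Bonferroni correction has been used for multiple testing". The row for the chosen size is "66 | 14.1 | 82.4 | 0.237": total n, power for 0.096 l, power for 0.243 l, and the difference detectable at 80% power. Neither the power formula nor the sidedness is named.

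Section 4.11.2 analyses outcomes by multiple linear regression. It tests the null hypothesis by ANOVA, examines the three pairwise differences for their size, and reports differences in means with 95% confidence intervals.

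**The concern.** A normal-approximation power formula treats the SD as known. In the planned analysis the SD is estimated from the residuals, so a pairwise difference is referred to a t distribution. With 20 to 25 infants per group and a Bonferroni-adjusted alpha, the t critical value is visibly larger than the normal one. The normal formula then overstates power and understates the detectable difference.

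The effect is greatest in the smallest rows of Table 3, which include the size the trial chose. A reader who sees 82.4% and 0.237 l would think there is a small reserve above 80% power for 1 SD. A few lost or unusable scans would matter more if that reserve is not there. The same table is offered for sizing a multicentre extension.

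**Working it through.** **Inputs.** SD 0.243 l, target difference 0.243 l (1 SD), 22 scanned infants per group in three equal groups, 5% overall alpha and a Bonferroni correction, all from 4.11.1. The number of comparisons, three, comes from 4.11.2, so alpha per comparison is 0.05/3 = 0.0167. Two-sided testing is an assumption; it is supported because it reproduces the table.

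**Step 1: reproduce the plan's figure.** Normal approximation: power = Φ(δ/(σ√(2/n)) − z), with z the two-sided critical value.

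- δ/(σ√(2/n)) = √(22/2) = 3.317.
- At alpha 0.05/3, z = 2.394, and Φ(0.923) = 82.2%.
- At alpha rounded to 0.017, z = 2.387, and Φ(0.930) = 82.4%, the printed value.
- Detectable difference at 80% power: (2.387 + 0.842) × 0.243 × √(2/22) = 0.237 l, as printed.

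With alpha 0.017 this formula matches every printed power in both power columns to 0.1 point, and the detectable-difference column to within 0.001 l. Other candidates do not give 82.4%: unadjusted alpha 0.05 gives 91.3% (normal) or 90.0% (two-sample t).

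**Step 2: replace the normal by the t distribution.** Power = P(T > t_crit), where T is noncentral t with noncentrality (δ/σ)√(n/2), and t_crit is the two-sided critical value at 0.05/3. With 22 per group:

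- Pooled residual error from three groups, 3 × 22 − 3 = 63 df: t_crit = 2.460, power 80.1%, detectable difference 0.243 l.
- Separate two-sample t-tests, 2 × 22 − 2 = 42 df: t_crit = 2.494, power 79.1%, detectable difference 0.246 l.
- Pooled error with three further df spent on covariates (60 df, an illustration): 80.0%.

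A simulation of 200,000 trials gave 80.1% (pooled) and 79.0% (two-sample).

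**Step 3: the neighbouring rows, for a 1 SD difference at alpha 0.05/3.**

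| Total n | Stated power | Pooled t | Gap (points) | Two-sample t | Stated detectable difference (l) | Pooled t (l) |
|---|---|---|---|---|---|---|
| 60 | 78.1% | 75.4% | 2.7 | 74.2% | 0.249 | 0.255 |
| 66 | 82.4% | 80.1% | 2.3 | 79.1% | 0.237 | 0.243 |
| 75 | 87.5% | 85.8% | 1.7 | 85.0% | 0.222 | 0.227 |
| 90 | 93.1% | 92.1% | 1.0 | 91.7% | 0.203 | 0.206 |

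At 66, about 0.2 of the 2.3 points comes from rounding alpha (82.4% to 82.2%); the rest comes from normal versus t. In the 0.096 l column the pooled gap is about 1 point or less (at 66, 14.1% stated and 13.3% recomputed).

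**Step 4: the overall F test.** At 5%, with 2 and 63 df and two groups 1 SD apart, the noncentrality is n × Σ(μᵢ − μ̄)²/σ².

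- Third group midway: 22 × (0.25 + 0 + 0.25) = 11.0, power 83.4%. This is the least favourable position between the other two.
- Third group equal to one of them: 22 × 2/3 = 14.7, power 92.8%.

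**The case against.** The strongest reply is that nothing printed is shown to be false. The table follows correctly from a standard large-sample formula, and the protocol names no other. The ANOVA is the planned test of the null hypothesis, and its F test has more power than the table states. Section 4.11.2 examines the pairwise differences for magnitude and does not carry the Bonferroni correction into the analysis. The text's claim, "with just over 80% power and at 5% significance level", survives with the pooled error that ANOVA or regression would use. Covariate adjustment could recover the difference: if covariates explained 2% of the variance, power with 60 df would be 80.9%, and at 5% it would be 82.3%. Those R-squared values are assumptions, since the documents give none. Finally, 4.11.1 calls the study primarily a feasibility pilot and accepts that it will likely be underpowered for adiposity.

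Most of this stands, and it limits the point in three ways.

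- A reader might infer that the trial's main test has only 79–80% power. It does not follow: that figure belongs to the Bonferroni pairwise comparisons, and the F test has at least 83.4% when the third group lies between two groups 1 SD apart.
- A reader might infer that the power statement in the text is wrong. It falls short, by about one point, only with separate two-sample t-tests, which the plan does not specify.
- A reader might call this an arithmetic error of 2 to 4 points in all the smaller rows. The sums are right for the formula used, and with pooled df the gap is 1.7 to 2.7 points for totals 60 to 75.

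The reply does not rescue the table itself. Table 3 is presented as Bonferroni-corrected, and for comparisons of that kind the t distribution is the relevant one.

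**Conclusion.** The point holds for Table 3 read as Bonferroni-corrected pairwise power. Its figures are slightly too favourable in the rows near the chosen size. At 66 scans, power for a 1 SD difference is 80.1% rather than 82.4%, and the detectable difference is 0.243 l rather than 0.237 l, a change of 6 ml. The chosen size therefore meets 80% power for 1 SD with essentially nothing to spare. From 90 upward the power error is about 1 point or less and would not alter a decision on an extension.

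This rests on two-sided testing, three comparisons at 0.05/3, equal groups of 22 scanned infants, a common SD of 0.243 l, and no gain from covariates. The importance is minor: a matter of stating the table accurately, with no bearing on the conduct of the pilot.

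**What to change.** Recompute Table 3 with the noncentral t distribution at alpha 0.05/3 and pooled residual degrees of freedom. State beside it the test, the sidedness, the alpha per comparison and the degrees of freedom. Restate the 66 row as about 80% power for 1 SD, with a detectable difference of 0.243 l. Add the power of the overall F test at 5% (83.4% with the third group midway, 92.8% with it equal to one of the other two), so that the planned test of the null hypothesis has its own figure.

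The cost is a revised table with slightly less favourable numbers; enrolment does not change. If the investigators wanted a margin, 23 scanned infants per group would give 82.2% with pooled error (81.2% with two-sample tests), but the point does not require it.

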4.11.2 Statistical analysis

Outcomes will be analysed both for by intention to treat and as per protocol using multiple linear regression with adjustment for covariates where appropriate. Baseline covariates such as gender, gestational age, and birthweight z score, will be controlled for by randomisation stratification, while those such as ethnicity will be adjusted for. To address the null hypothesis differences between groups will be tested using ANOVA, with examination of the 3 pairwise differences for magnitude of differences. For the purposes of modelling randomised babies will be assigned to categories of overall intake (predominantly MOM, predominantly PTF, predominantly HDM). Results will be presented as estimates and 95% confidence intervals for differences in means.

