2.2.2 Human milk versus preterm formula: metabolic consequences

The association between low birth weight and later adult metabolic disease such as type-2 diabetes is now well established (6,7). Epidemiological studies show an association between low birth weight and decreased lean mass, increased total adiposity, and increased central adiposity in adults (8) ,a body composition which has consistently been linked with later insulin resistance (9). Third trimester and early postnatal growth appears to have a major impact on this later adult metabolic phenotype. Longitudinal growth data indicate that those born small for gestational age but then show catch up growth, specifically from birth to 3 months, are most at risk of later insulin resistance in young adulthood (10)

Prematurity, regardless of fetal growth, has been associated with later insulin resistance in adults (11). Using whole body MRI, our group has shown that the preterm born adult phenotype is characterised by increased total and abdominal adiposity compared to term born controls (12). As early as at term equivalent age we have shown that there is aberrant deposition of adipose tissue, with an excess of intra-abdominal adipose tissue, and reduced lean body mass in preterm infants in comparison to their term-born counterparts, with illness severity being the major determinant of adiposity (13). Although the neonatal morbidities associated with preterm birth may well contribute to long term metabolic health, mounting evidence highlights the impact of early growth velocity during postnatal third trimester growth.

Follow-up to early adulthood of preterm babies recruited to landmark nutritional trials in the early 1980s by Lucas and colleagues showed lower insulin resistance at adolescence in preterm infants randomised to receive standard formula compared to a growth promoting enriched formula (14) , those infants with the greatest growth velocity in the first 2 weeks of life having the greatest insulin resistance at adolescence. Consistent with these findings, Roteveel et al have recently shown that preterm infants who had highest early postnatal growth velocities had highest insulin resistance as young adults regardless of prior fetal growth (15).

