4.6 Randomisation

Randomisation will be generated centrally using a computer program, with minimisation by infant sex, gestational age (25-27+6 wks, 28-31+6 wks) birth-weight Z score (<-1.28, >-1.28) Randomisation will take place between 24-48hrs of age. Infants will be randomised to receive either HDM or PTF to make up any shortfall in Mother's Own Milk (MOM) until 34+6 weeks postmenstrual age. Blinding of the intervention is not practicable because of the distinctive appearances of human milk and formula, and the method of administration to preterm babies by syringe and nasogastric tube. At 35 weeks, the infant will be close to discharge, and feeding will be directly from the breast or formula by bottle in accordance with maternal choice.

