4.9.3 Randomisation

- Study number
- Date and time of birth
- Gender
- Confirmation of eligibility (full eligibility check)
- Date of parental consent
- Name of person taking consent
- Gestational age (in weeks and days)
- Recruiting hospital
- Allocated trial intervention (HDM or PTF)

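### Section 4.11.2 leaves the three minimisation factors out of the primary model, so if they predict adiposity the 95% intervals are too wide and the ANOVA is conservative

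*Combined protocol and SAP*

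**What the plan says.** Section 4.6 generates the allocation centrally, "with minimisation by infant sex, gestational age (25-27+6 wks, 28-31+6 wks) birth-weight Z score"; the protocol summary lists the same three factors. Section 4.11.2 provides for multiple linear regression with covariates as appropriate, and then says how particular covariates are handled: "Baseline covariates such as gender, gestational age, and birthweight z score, will be controlled for by randomisation stratification". Variables outside the minimisation are treated differently in the same sentence: "while those such as ethnicity will be adjusted for". The null hypothesis is tested by ANOVA across the three arms, the three pairwise differences are examined for size, and results are given as differences in means with 95% confidence intervals.

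No other section puts sex, gestational age or birthweight z score into the model, and no re-randomisation test is planned.

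Section 4.11.1 sets the target: "28 infants will be recruited in to each of the three groups or until 22 infants in each group has had their MRI". It also says that "one of the aims of the study is to obtain data on the magnitude of effect on total body adiposity", and expects the study to be underpowered for this outcome.

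**The concern.** Section 4.11.2 treats balance at randomisation as a substitute for adjustment in the analysis. Minimisation makes the arms alike on the three factors, so to the extent that these predict adiposity, the difference between arms varies less from trial to trial. An analysis that omits the factors does not see this. Their between-infant variance stays in the residual, and the standard error is computed as if the arms could have differed on them freely.

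The consequence is conservative: the treatment estimates are unbiased and false positives are not inflated. What is at stake is precision. The effect estimate and its interval are a stated product of this pilot, and the intervals would be wider than the data justify.

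**Working it through.** **Inputs from the documents**
- SD of total body adiposity 0.243 l; design difference 0.243 l, that is 1 SD (4.11.1).
- 28 infants per arm recruited (84) and 22 per arm scanned (66); 22/0.8 = 27.5, rounded up to 28 (4.11.1).
- Bonferroni correction in Table 3, taken as 0.05/3 two-sided for three pairwise comparisons.
- Three binary minimisation factors (4.6).

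**Inputs assumed, because the documents do not give them**
- Share of adiposity variance explained by the three factors together (R²): 0, 0.1, 0.2 or 0.3, split equally among them.
- Prevalence: 50% for sex, 35% for the lower gestational age band, 12% for z score below -1.28.
- Minimisation assigns the best-balancing arm with probability 0.8, otherwise an arm at random.
- Loss from 84 to 66 is random. Ethnicity is omitted from both models.

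**Step 1: the plan's own figure.** Pairwise standard error = 0.243 × √(2/22) = 0.0733 l. Difference/SE = 0.243/0.0733 = 3.317. The critical value at 0.05/3 two-sided is 2.394. Power = Φ(3.317 − 2.394) = 82.2%, against 82.4% in Table 3. The plan's figure reproduces and is not disputed.

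**Step 2: direction, by formula.** With perfect balance among the infants analysed, the true variance of a pairwise difference is (1 − R²) × SD² × 2/n. The unadjusted analysis reports about SD² × 2/n. Reported/true SE = 1/√(1 − R²) = 1.05, 1.12 and 1.20 for R² = 0.1, 0.2 and 0.3. The approximate size of the 5% F test on 2 and 63 df is then 3.7%, 2.5% and 1.5%. These are limiting values; the random element in minimisation and later losses soften them.

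**Step 3: simulation of the design** (20,000 replicates per row; SE in SD units).

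| R² | F-test type I error, without / with factors | Reported / true SE without factors | Ratio | Coverage of 95% interval without factors | Reported SE with factors | Pairwise power for 1 SD at 0.05/3, without → with |
|---|---|---|---|---|---|---|
| 0 | 5.1% / 5.0% | – | – | – | – | 80.0% → 79.4% |
| 0.1 | 4.1% / 5.2% | 0.302 / 0.292 | 1.03 | 95.7% | 0.288 | 81.0% → 84.0% |
| 0.2 | 3.1% / 5.0% | 0.302 / 0.280 | 1.08 | 96.6% | 0.272 | 81.4% → 88.2% |
| 0.3 | 2.3% / 5.0% | 0.303 / 0.270 | 1.12 | 97.2% | 0.254 | 82.2% → 92.3% |

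With fully deterministic minimisation, the unadjusted type I error is 3.8%, 3.0% and 2.1% for R² = 0.1, 0.2 and 0.3.

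**Step 4: interval width.** Half-width = 0.243 × SE × t(0.975), where t is about 2.00 on 63 or 60 df.
- Without the factors: 0.243 × 0.302 × 2.00 = 0.147 l.
- With the factors: 0.243 × 0.288 × 2.00 = 0.140 l; 0.243 × 0.272 × 2.00 = 0.132 l; 0.243 × 0.254 × 2.00 = 0.123 l.

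**Step 5: sensitivity and control** (4,000 replicates, z-score prevalence 15%).
- R² = 0.2: unadjusted SE 0.0735 l against a true 0.0670 l (10% too large), size 2.8%; adjusted SE 0.0660 l, size 4.6%.
- R² = 0.4: unadjusted SE 0.0735 l against 0.0636 l (16% too large), size 1.7%; adjusted SE 0.0571 l, size 5.4%.
- Without minimisation (simple equal allocation), R² = 0.4: unadjusted size 5.0%. The distortion therefore comes from balancing without adjusting.

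**The case against.** **This is efficiency, not validity, in a feasibility pilot that already concedes low power.** True, and it sets the rank of the point. It does not remove it: the plan still specifies a null-hypothesis test and 95% intervals, and both are off their nominal level whenever the factors matter.

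**The size depends wholly on an assumed R².** This stands. Section 2.2.2 describes preterm adiposity "with illness severity being the major determinant of adiposity", and illness severity is not a minimisation factor. Under the assumed prevalences and equal shares, the difference between factor levels is 0.243 × √(R²/(3p(1 − p))). At R² = 0.1 that is 0.089 l for sex, 0.093 l for gestational age band and 0.137 l for z-score band. These are of the order of the 0.096 l difference in Table 3. At R² = 0.05 the effect is negligible: type I error 4.5%, SE about 1% too large, pairwise power 80.1% against 80.6% adjusted.

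**The power gain for the planned test is smaller than for the pairwise tests.** This also stands. Section 4.11.2 tests by ANOVA; Bonferroni pairwise power is the basis of Table 3. With one arm shifted by 1 SD, F-test power rises from 92.7% to 94.3%, 93.1% to 96.7% and 94.1% to 98.4% at R² = 0.1, 0.2 and 0.3. The gains are about 1.6, 3.6 and 4.3 points; other patterns of means would give other gains.

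**The simulation simplifies.** It leaves out ethnicity, uses binary factors only and assumes random loss, whereas deaths, unstable infants and separate consent for the scan make real losses less tidy. Heavier loss would weaken the balance and shrink the distortion, but not reverse it or remove the precision gained by adjusting.

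**The general clause on covariates might let the factors in.** The contrast with ethnicity makes exclusion the natural reading. If inclusion was meant, the text is ambiguous about the primary model and needs the same edit.

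**Conclusion.** The concern holds, conditionally on the factors being prognostic. The direction follows from the design; the size is an assumption. For R² between 0.1 and 0.3, the plan as written overstates the standard error by 3% to 12% and runs the ANOVA at 4.1% to 2.3% instead of 5%. It forgoes about 3 to 10 points of Bonferroni pairwise power, or about 2 to 4 points for the F test with one arm shifted. At R² of 0.05 or less there is little or no distortion. Bias, false-positive inflation and the Table 3 figures are not in question. The change is recommended, not essential. Choosing these factors for balance makes sense mainly if they are thought to be prognostic, and that is when they should be in the model.

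**What to change.** In section 4.11.2, delete the statement that these covariates are controlled for by the randomisation. Specify the primary analysis as one linear model (ANCOVA) of total body adiposity on arm, sex, gestational age and birthweight z score, with the ethnicity adjustment already planned. Gestational age and z score are preferably continuous. Test arm with the 2-df F test from that model at 5%, and take the three pairwise estimates and 95% intervals from the same model.

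No new data are needed: sex and gestational age in weeks and days are recorded at randomisation (4.9.3) and birth weight at baseline (4.9.4). The cost is about 3 residual degrees of freedom, from 63 to 60 with 66 infants before ethnicity. If the factors explain nothing, pairwise power falls by about 0.6 points (80.0% to 79.4%).

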2.4 Importance to the NHS

Infant nutrition studies involving randomisation, testing causality and unravelling biological mechanisms are rare. Yet infant nutrition is a cardinal candidate effector of long-term health. Current practice in feeding the preterm infant invariably involves the use of fortified Human Donor Milk or Preterm Formula. There are however no national standards or guidelines for enteral feeding of extremely preterm infants, and clinical practice is very variable.

Advocates of pasteurised HDM believe this is as efficacious as MOM in reducing two of the most feared conditions in newborn medicine, necrotising enterocolitis and bloodstream infection, and in improving long-term metabolic health. These result in major health services utilisation costs and a life-long burden of impairments on survivors.

An adequately powered trial is required to address these outcomes but poses two major hurdles, recruitment of large numbers of babies, and long-term follow-up. The organisation of NHS neonatal specialist care and the establishment of the Neonatal Data Analysis Unit that holds and archives national neonatal data at Chelsea & Westminster Hospital, and has received permission for the National Information Governance Board to link this to Hospital Episode statistics data, offers unique international opportunity to conduct this trial in the UK and achieve long term follow-up at low cost. Clarification of efficacy will advance clinical care, and enable economic evaluation and rational development of Human Milk Banking.

3. Aims and Hypothesis

Specific aims of this pilot trial are to:

A: Assess feasibility

- 1) test the acceptability of the trial design with parents and clinicians
- 2) test that recruitment to target is achievable, estimate consent and dropout rates
- 3) estimate the trial requirement for HDM from NHS Human Milk Banks
- 4) test that clinical outcome data can be retrieved from operational NHS electronic records, thus minimising the burden of data capture and facilitating the use of linked NHS records to achieve long-term follow-up at low cost.

B: Obtain data on the magnitude of effect at term equivalent age and again at term plus 6 weeks of age, on key mechanistic outcomes:

- 1) the primary outcome of total body adiposity, addressing the null hypothesis: there are no differences in total body adiposity, as measured by whole body MRI, between infants randomised to receive fortified MOM+/-HDM, unfortified MOM+/-HDM, or MOM+/-PTF.

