- 2) the secondary outcomes of
 - Regional adiposity, as measured by whole body MRI
 - Non adipose tissue, as measured by whole body MRI
 - Total brain volume, as measured by MRI
 - Anthropometry (weight, length, and head circumference)
 - IHCL, as measured by magnetic resonance spectroscopy
 - blood pressure
 - Stool and urine metabolomic profile
 - Blood Quantitative Insulin Sensitivity Check Index (QUICKI) – at discharge only between infants randomised to receive fortified MOM+/-HDM, unfortified MOM+/- HDM or MOM+/-PTF.

C: By using HDM with known macronutrient content, we aim to correlate macronutrient intake of each intervention with the above outcomes.

4. Methods

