4.9.4 Baseline evaluation

- Birth weight (kg)
- Birth length (cm)
- Head circumference (cm)
- Ethnicity (NHS ethnicity)
- Mother's date of birth
- Mother's ethnicity
- Mother's height and weight (collected on case report form)
- Father's ethnicity
- Father's height and weight (collected on case report form)
- Mode of delivery
- Use of antenatal steroids
- Diastolic blood pressure
- Systolic blood pressure
- Medical conditions and perinatal medications
- Metabolomic profile (urine and stool) after informed consent

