4.9.9 Scan visits

Data will be collected at each scan visit on the following:

- Weight
- Length
- Head circumference
- Feeding data (see below)
- Urine and stool for metabolomic profile

Urine samples (1 ml, from cotton wool placed in the nappy), and stool specimens (from the nappy) will be collected immediately after recruitment and at both scan appointments. All samples will be analysed at Imperial College using high throughput techniques employing in vitro NMR. This aspect of the proposed research will be supervised by [name], a leading international authority in the field.

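### Section 4.11.2 does not commit to adjusting weight, length and head circumference for the infant's own birth value, so the growth comparisons are likely to be less precise than the collected data allow

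*Combined protocol and SAP*

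**What the plan says.** Weight, length and head circumference are secondary outcomes (section 1 and section 3, Aim B). Aim B is to "Obtain data on the magnitude of effect at term equivalent age and again at term plus 6 weeks of age". Section 4.9.9 lists the three measures among the items for which "Data will be collected at each scan visit on the following". The baseline list in section 4.9.4 includes birth weight, birth length and head circumference.

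Section 4.11.2 analyses outcomes "using multiple linear regression with adjustment for covariates where appropriate". It then divides the covariates into two groups. On the first it says: "Baseline covariates such as gender, gestational age, and birthweight z score, will be controlled for by randomisation stratification". On the rest it says: "while those such as ethnicity will be adjusted for". No section says that an outcome's own birth value enters its model.

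The minimisation in section 4.6 uses sex, gestational age in two bands (25 to 27+6 and 28 to 31+6 weeks) and birthweight z score in two bands (cut at -1.28). Birth length and birth head circumference are not factors.

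**The concern.** The pilot reports estimates with 95% confidence intervals, so the width of those intervals largely decides how useful its growth results are. Growth is also central to the clinical question: sections 2.2.4 and 2.2.5 describe slower growth on human milk than on preterm formula, even with fortification.

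The measurement at birth is the obvious covariate for a later measurement of the same quantity. The plan collects it but does not say that it will be used. What it relies on instead is coarse. The gestation bands span 21 and 28 days, every infant above a z score of -1.28 is treated alike, and neither factor measures length or head size directly. With about 22 infants per arm, chance differences in birth size can remain within those bands, and an unadjusted model carries them into the later comparison as noise.

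The covariate list is also open in a trial that section 4.6 describes as unblinded. Covariates could therefore be chosen after results by arm are known. Naming them in advance removes that doubt.

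**Working it through.** **Inputs from the documents.** Three arms, with 22 infants per arm scanned, 66 in all (section 4.11.1). The plan gives no variance, target difference or power for any growth measure.

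**The plan's own figure.** The only power basis is for adiposity. For a difference of 1 SD with 22 per arm and a two-sided 0.05/3 level (taking the Bonferroni correction as three pairwise comparisons), the standardised difference is 1/√(2/22) = 3.317. Subtracting the critical value 2.394 leaves 0.923, which is a power of 82.2%. Table 3 gives 82.4%. The figure reproduces, but it says nothing about growth. It is used here only to confirm the group size.

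**Input that has to be assumed.** Let r be the correlation between the birth value and the later value of the same measure, given arm and gestational age. The documents do not state it, so a range is shown. It has to be the correlation given gestational age because length and head circumference in centimetres depend on gestation at birth, and gestational age is in the proposed model.

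**Formula.** Adjustment multiplies the residual variance by 1 - r². Estimating one covariate slope with 66 infants in three arms costs a factor of 1 + 1/(66 - 3 - 2) = 1 + 1/61. The standard error relative to the model without the birth value is therefore √[(1 - r²)(1 + 1/61)].

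The unadjusted half-width of a pairwise 95% interval is 2.00 × √(2/22) = 0.60 outcome SDs. The last column multiplies this by the ratio.

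| r | 1 - r² | SE ratio | Change in SE | Half-width (SDs) |
|---|---|---|---|---|
| 0 | 1.00 | 1.008 | +0.8% | 0.61 |
| 0.1 | 0.99 | 1.003 | +0.3% | 0.60 |
| 0.2 | 0.96 | 0.988 | -1.2% | 0.60 |
| 0.3 | 0.91 | 0.962 | -4% | 0.58 |
| 0.5 | 0.75 | 0.873 | -13% | 0.53 |
| 0.7 | 0.51 | 0.720 | -28% | 0.43 |

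**Break-even.** The ratio is 1 when 1 - r² = 61/62 = 0.984, so r² = 0.016 and r is about 0.13. Below that, adjustment costs at most 0.8% of the standard error.

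**Two covariates.** With gestational age also in the model, the factor is 1 + 2/(66 - 3 - 3) = 1 + 2/60 = 1.033. If neither variable predicted the outcome, the standard error would rise by √1.033 - 1, about 1.7%.

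**Sensitivity to the number of infants.** Section 4.1 takes anthropometry from routine data, so more than 66 infants may contribute at term. With all 84, the one-covariate factor is 1 + 1/79, and the ratio at r = 0.5 is √(0.75 × 1.0127) = 0.871, practically the same.

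**The case against.** The strongest objection is that the plan excludes nothing. Section 4.11.2 allows adjustment where appropriate, and both covariate lists are illustrative. Birth length and head circumference are baseline variables outside the minimisation, so on the plan's own division they fall most naturally among those to be adjusted for. This stands. A reader might infer that the growth outcomes will not be adjusted for size at birth, but the text supports only that such adjustment is not specified.

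Second, the gain is not established. It rests on a partial correlation that the documents do not give, and below about 0.13 there is none. This also stands, so the plan cannot be called needlessly imprecise as a matter of fact.

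Third, the minimisation gives some indirect balance, because gestation and birthweight both relate to length and head size. That is true, and it limits chance imbalance. It does not recover the precision that a continuous covariate in the model would give.

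Fourth, baseline values may be incomplete. Table 2 marks them as routine-care measurements, section 4.9.1 takes such data from the national database, and Aim A treats retrieval of clinical outcome data from NHS records as a question to be tested. A complete-case analysis could lose infants and offset the gain. The objection is sound, and the fix must deal with it.

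Finally, these are secondary outcomes in what section 4.11.1 calls primarily a feasibility pilot, and no growth hypothesis is powered. That limits the weight of the point but does not remove it.

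**Conclusion.** The point holds as a gap in specification with a probable cost in precision. The plan does not commit to using each growth measure's own birth value; it relies on two-level minimisation for gestation and birthweight z score and names only ethnicity for adjustment. For a correlation of 0.3 to 0.7 given gestational age, using the birth value would reduce the standard error by about 4% to 28%; at zero correlation it would add about 1%. These figures assume 66 infants, a linear relation and birth values available for all of them.

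A reader might infer that the growth comparisons are biased. They are not: under randomisation an unadjusted comparison remains valid, and precision is what is at stake. Nor does this point bear on the primary adiposity outcome, which has no birth measurement of its own in the plan. It is a nearly free improvement to secondary analyses in a pilot.

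**What to change.** In section 4.11.2, state that weight, length and head circumference at each time point will be analysed by linear regression on:

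- randomised arm;
- the infant's own birth value of that measure, as a continuous variable or as a z score for gestation and sex;
- gestational age at birth, as a continuous variable.

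Add that missing birth values will be handled by simple baseline imputation or a missing-value indicator, so that no randomised infant with an outcome is dropped.

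The cost is two or three sentences and two degrees of freedom, plus one more if an indicator is used. No new data are needed.
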